11.2.3. Equipment is operating inconsistently or is deemed unsafe

Protocol Name:	Investigational Study of the Ekso Bionics Powered Exoskeleton for High-Dosage Use by Individuals with Spinal Cord Injury in a Non-Clinical Environment
Principal Investigator:	[name], Sr. Controls Engineer
Primary Contact Name/Contact Info:	[name], Sr. Controls Engineer [contact] [contact]
Date Revised:	9/28/2015
Study Number:	13098-01

11.2.4. A therapist/researcher involved feels that the subject's performance or continued usage places them at risk for injury.

11.2.5. The subject is experiencing any adverse medical condition as evaluated by the subject, clinician or spotters.

11.2.6. The subject or assistants to the subject (spotter or otherwise), deliberately or not, does not follow the study protocol or uses or permits use of the device in an unsafe manner.

11.3. If the subject, deliberately or not, does not follow the study protocol or uses or permits use of the device in an unsafe manner, the device may be returned to Ekso Bionics without financial reconciliation to the subject.

11.4. If the subject does not walk in the Ekso for a period of more than 21 days for any reason, they will be withdrawn from the investigation.

11.4.1. If the subject wishes to resume participation in the study, additional training of the subject and baseline assessments may be necessary.

12. Procedures Involved in the Human Research

12.1. The study is designed to enable Ekso Bionics to evaluate the high-dosage use of a robotic exoskeleton in the home environment by persons with spinal cord injury. The study is based on the existing Ekso device. Features will include devices and controls to emulate proper gait training, stability and walking for common daily function. The device will not allow all daily functions including bending over, squatting, toilet use, climbing up or down stairs or ramps, side stepping or backward stepping.

Protocol Name:	Investigational Study of the Ekso Bionics Powered Exoskeleton for High-Dosage Use by Individuals with Spinal Cord Injury in a Non-Clinical Environment
Principal Investigator:	[name], Sr. Controls Engineer
Primary Contact Name/Contact Info:	[name], Sr. Controls Engineer [contact] [contact]
Date Revised:	9/28/2015
Study Number:	13098-01

12.2. Since the study involves periodic observation and data collection for evaluation by Ekso Bionics clinical, engineering and marketing personnel, the testing procedures includes:

12.2.1. Periodic evaluations by trained Ekso Bionics clinicians according to general inclusion/exclusion criteria.

12.2.2. A minimum of weekly electronic data transfer to Ekso Bionics of the data collected on the Ekso on-board computer. These data includes but are not limited to

12.2.3. Number of steps.

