6.1.14. Bone Density - DEXA Scan (Initial and 12 month)

6.2. The subject will identify an individual to spot them for safety during every moment of device use. The individual may be a relative, friend or an individual hired by the subject. The spotter will not likely be a medical professional although Ekso Bionics will consider a medical profession as a spotter. The spotter must meet the Inclusion/Exclusion criteria listed below. Ekso Bionics clinicians will train the spotter with the subject in the device over a three day period in the subject's home environment (Appendix A). The spotter must be certified as

	Protocol Name:	Investigational Study of the Ekso Bionics Powered Exoskeleton for High-Dosage Use by Individuals with Spinal Cord Injury in a Non-Clinical Environment
	Principal Investigator:	[name], Sr. Controls Engineer
	Primary Contact Name/Contact Info:	[name], Sr. Controls Engineer [contact] [contact]
	Date Revised:	9/28/2015
	Study Number:	13098-01

competent by Ekso Bionics' clinicians in order for the device to be used without an Ekso Bionics clinician present. If the spotter is not approved, the subject may locate another spotter. Due to the time commitment required of the spotter, each subject may choose to train up to two spotters during the initial spotter training sessions.

6.3. Subject training will include but is not limited to:

- 6.3.1. Informing of device functions, failure modes and common characteristics.
- 6.3.2. Safety and how to respond to various conditions including being off balance, uneven surfaces.
- 6.3.3. Device set-up and take-down
- 6.3.4. Operating the device.
- 6.3.5. Putting the device on and taking the device off.
- 6.3.6. Sitting/Standing
- 6.3.7. Walking
- 6.3.8. Balance
- 6.3.9. Using hands when in the device

6.4. Spotter training will include but is not limited to:

- 6.4.1. Informing of device functions, failure modes and common characteristics.
- 6.4.2. Safety and how to respond to various conditions including being off balance, uneven ground.
- 6.4.3. Device set-up and take-down
- 6.4.4. Operating the device.
- 6.4.5. Putting the device on and taking the device off.
- 6.4.6. Sitting/Standing
- 6.4.7. Walking
- 6.4.8. Supporting the subject

Protocol Name:	Investigational Study of the Ekso Bionics Powered Exoskeleton for High-Dosage Use by Individuals with Spinal Cord Injury in a Non-Clinical Environment
Principal Investigator:	[name], Sr. Controls Engineer

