12.2.4. Length of steps

12.2.5. Speed

12.2.6. Walking mode used

12.2.7. Battery usage

12.2.8. A minimum monthly transmittal of a usage log completed daily by both the subject and the spotter. The log will include subjective and objective data including (Appendix D):

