12.3.1. Donning/doffing the device

12.3.2. Standing/sitting

Protocol Name:	Investigational Study of the Ekso Bionics Powered Exoskeleton for High-Dosage Use by Individuals with Spinal Cord Injury in a Non-Clinical Environment
Principal Investigator:	[name], Sr. Controls Engineer
Primary Contact Name/Contact Info:	[name], Sr. Controls Engineer [contact] [contact]
Date Revised:	9/28/2015
Study Number:	13098-01

- 12.3.3. Walking
- 12.3.4. Balance and stability
- 12.3.5. Maneuverability
- 12.3.6. Duration of sessions
- 12.3.7. Device reliability
- 12.3.8. Physical and psychological deviations
- 12.3.9. Human factors and usability

13. Cost and Compensation

13.1. Equitable access plan:

There is a substantial cost to enrolling a subject in the study. The costs fall into four categories:

1. Training cost
2. Testing costs
3. Subject/Spotter costs
4. Device cost

Ekso will entirely bear the training cost (1) and cost associated with data acquisition (e.g. Dexa scan) (2). The subject will be responsible for the potential cost of obtaining a medical release from their physician. The subject will also be responsible for providing a spotter since this will often be an unpaid family member and therefore have no associated cost (3). The Ekso device (\$130,000-160,000 retail depending on features) is a substantial cost which some subjects will not be able to pay, nor can Ekso afford to provide enough devices for the desired number of subjects (4). Since Ekso Bionics' objective is to study the objectives in Section 3, the device will be equally accessible to all qualified subjects at cost. This will be achieved by one of the following options.

Protocol Name:	Investigational Study of the Ekso Bionics Powered Exoskeleton for High-Dosage Use by Individuals with Spinal Cord Injury in a Non-Clinical Environment
Principal Investigator:	[name], Sr. Controls Engineer
Primary Contact Name/Contact Info:	[name], Sr. Controls Engineer [contact] [contact]
Date Revised:	9/28/2015
Study Number:	13098-01

13.1.1. Subjects may purchase their own Ekso device which they may then keep at the end of the study. This will enable a prompt start to their participation in the study.

13.1.2. Ekso will introduce subjects to non-profit organizations specifically available to fund robotic medical devices. These organizations include but are not limited to the Bridging Bionics Foundation

(<https://www.facebook.com/bridgingbionics?ref=stream>,

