16.1. The risk of falling: This could be caused by loss of control of the ambulation activity by the participant or spotter as well as malfunction of the Ekso device itself. The risk of falling will be minimized by having a trained spotter with the subject at all times. The risk of falling is further mitigated by allowing only very experienced subjects who have been approved by the Ekso Bionics Clinical Team walk in the device during the study. This risk is similar to any gait therapy in which subjects with lower extremity disorders are standing and walking.

16.2. Risk of exceeding subject range of motion: This would be caused if the Ekso moved the subject beyond their normal range of

Protocol Name:	Investigational Study of the Ekso Bionics Powered Exoskeleton for High-Dosage Use by Individuals with Spinal Cord Injury in a Non-Clinical Environment
Principal Investigator:	[name], Sr. Controls Engineer
Primary Contact Name/Contact Info:	[name], Sr. Controls Engineer [contact] [contact]
Date Revised:	9/28/2015
Study Number:	13098-01

motion, resulting in a strain, sprain and/or fracture. This risk is mitigated by mechanical hard stops that prevent the device from exceeding a normal human range of motion even in the event of a failure in the electrical or software systems. Software systems are also in place to further reduce range of motion to improve fit and comfort for subjects during walking. Subjects will be evaluated by trained Ekso Bionics clinicians who will eliminate any subjects from participation if they cannot meet the required range of motion.

16.3. Discomfort, skin pressure/friction, bruising, pain, or unusual swelling caused by the exoskeleton which has the potential to lead to skin breakdown or abrasions. All locations where the subject contacts the exoskeleton are padded to prevent bruising or skin irritations. Also all pinch points are covered and protected from catching either skin or clothing. Adjustments to the harness placement and additional padding will be assessed to decrease the risk of skin breakdown as well.

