19.1. Each participant will be assigned a coded identification number to designate all evaluations. Data will be stored by the coded identification number without information identifying the individual. All data, written and electronic, will be stored on

Protocol Name:	Investigational Study of the Ekso Bionics Powered Exoskeleton for High-Dosage Use by Individuals with Spinal Cord Injury in a Non-Clinical Environment
Principal Investigator:	[name], Sr. Controls Engineer
Primary Contact Name/Contact Info:	[name], Sr. Controls Engineer [contact] [contact]
Date Revised:	9/28/2015
Study Number:	13098-01

the Ekso Bionics server with password protection. Data will only be available to the researchers involved in the studies.

20. Payments to Subjects

No payments will be provided.

21. Consent Process

21.1. Ekso Bionics will require all participants to sign an Ekso Bionics Medical Release/Consent Form and Permission to Obtain Medical Treatment prior to the preliminary evaluation. Spotters will be required to sign an Ekso Bionics Consent Form:

21.1.1. All consent information will be provided to the subject in advance of their clinical screening.

21.2. There will be no waiting period required between the subjects being informed of risks and their providing of consent for participation in the study. Payment for the device must be received in most cases prior to starting the study.

22. Informed Consent Process for Research

22.1. The consent process will be directly conducted by a member of the Ekso Bionics clinical team who is under the direct supervision of [name], Ekso Bionics' Clinical Director. The consent process typically takes 30-60 minutes for the subject to understand and consent to participate in the study.

22.2. Only test subjects capable of comprehending and acknowledging the consent form will be included in the test.

	Protocol Name:	Investigational Study of the Ekso Bionics Powered Exoskeleton for High-Dosage Use by Individuals with Spinal Cord Injury in a Non-Clinical Environment
	Principal Investigator:	[name], Sr. Controls Engineer
	Primary Contact Name/Contact Info:	[name], Sr. Controls Engineer [contact] [contact]
	Date Revised:	9/28/2015
	Study Number:	13098-01

Appendices

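### Section 11.3 gives a subject who bought the device a financial reason not to disclose inadvertent unsafe use, which can bias the home-safety and spotter-safety findings towards safe

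*Protocol*

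**What the plan says.** Section 11.3 of the Protocol sets the condition: "If the subject, deliberately or not, does not follow the study protocol or uses or permits use of the device in an unsafe manner". It then sets the consequence: "the device may be returned to Ekso Bionics without financial reconciliation to the subject". It makes no exception for purchased devices and does not mention events that are reported in good faith.

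Section 13.1.1 gives one of three ways to obtain a device: "Subjects may purchase their own Ekso device which they may then keep at the end of the study". The other two (13.1.2 and 13.1.3) are non-profit funding and a fundraising programme. Section 13.1 gives the price in dollars as "130,000-160,000 retail depending on features". It adds that subjects get access at cost, but does not state that cost. Section 21.2 says: "Payment for the device must be received in most cases prior to starting the study".

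On the record of home use, 12.2.8 requires "A minimum monthly transmittal of a usage log completed daily by both the subject and the spotter". On the spotter, 6.2 says: "The individual may be a relative, friend or an individual hired by the subject". Section 17.1 has the spotter call medical services when these are needed, and says that the principal investigator should also be contacted once the subject is stable.

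Objectives 3.3 and 3.4 are to establish safety and efficacy in the home and with a spotter who is not a medical professional.

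**The concern.** Two of the study's objectives are safety questions about what happens when no sponsor clinician is present. The people best placed to report those events are the subject and a companion the subject has picked. Section 11.3 attaches a possible loss of the device, with no money back, to conduct that these people would have to disclose, and it attaches the loss whether or not the conduct was intended.

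Falls come into this indirectly. Section 16.1 says of a fall: "This could be caused by loss of control of the ambulation activity by the participant or spotter", and also names device malfunction. Section 7 (environmental conditions) rules out several ordinary domestic surfaces, such as deep-pile carpet and grass, so an unintended breach is easy to foresee. A full account of a fall may therefore disclose inadvertent unsafe use or a protocol departure.

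If some such accounts are withheld or trimmed, the safety conclusions err in one direction. The sponsor also fails to learn of hazards that other homes may share. With at most twelve subjects (section 9), a few missing reports would matter.

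**Working it through.** The protocol gives no event rate, reporting rate or safety threshold, so it has no figure to reproduce. The check has two parts: a reading of the sections together, and an illustration on assumed inputs.

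**Reading the sections together**

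1. *Who can lose money.* 11.3 covers every subject. Only those who paid for the device themselves (13.1.1) have their own money fully at stake. The ceiling is the retail price, and less if the device is sold at cost.
2. *What triggers the loss.* Protocol departure, or using or permitting unsafe use, by the subject, with or without intent. A fall is not listed.
3. *Who reports.* The daily log comes from subject and spotter (12.2.8), and contact after an injury runs through the spotter (17.1).
4. *What else could reveal an event.*
   - On-board data (12.2.2 to 12.2.7): steps, step length, speed, mode and battery, in a list that is not exhaustive. Transfer is at least weekly here, but 14.6 says at least once during the study.
   - Remote data (14.3): forces, torque, and position bearing on balance.
   - Clinician evaluations (12.2.1), possible checks at weeks 3 and 7, and reviews at least every three months that are meant to assess safety (6.6).
   - Comparison of suspicious data with videos and pictures, or ignoring such data (14.8).

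   None of these is stated to detect falls or unsafe use, or to be reconciled with the log. The log items listed in 12.2.8.1 to 12.2.8.5 do not name falls either; the form itself is in Appendix D, which is not shown.
5. *Direction.* Nothing in 11.3 rewards reporting, so its effect can only be towards fewer reports.

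**Illustration (assumed inputs)**

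Let p be the true risk that a subject has at least one fall and r the chance that it is reported. Both are assumptions. With n = 12 (the maximum in section 9), the chance that at least one such subject is reported is 1 − (1 − pr)^12. At p = 0.20:

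- r = 1: 1 − 0.80^12 = 0.931
- r = 0.75: 1 − 0.85^12 = 0.858
- r = 0.5: 1 − 0.90^12 = 0.718

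Over p = 0.10 to 0.30 the range is 0.718 to 0.986 at r = 1, and 0.460 to 0.858 at r = 0.5.

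If none of the 12 is reported, the one-sided 95% upper limit for the true risk is (1 − 0.05^(1/12))/r: 22.1% at r = 1, 29.5% at r = 0.75 and 44.2% at r = 0.5.

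These figures apply r to all twelve subjects. Suppose instead that only two bought their device and report with r = 0.5, and the other ten report everything. At p = 0.20 the chance of at least one report is 1 − 0.80^10 × 0.90^2 = 1 − 0.1074 × 0.81 = 0.913. The upper limit after no reports solves (1 − p)^10 × (1 − p/2)^2 = 0.05, which gives p = 24.0%. The effect therefore depends heavily on how many subjects own their device, and the protocol does not fix that number.

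**The case against.** The strongest reply is that 11.3 penalises unsafe use and says nothing about reporting. Several parts of this reply stand.

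- *The trigger is narrower than it looks.* A reader might infer that a fall, or a lapse by the spotter, itself costs the subject the device. The text does not support this. Section 16.1 treats falling as a foreseen risk, with malfunction among its causes. Section 11.3 names only the subject, whereas 11.2.6 expressly adds assistants such as the spotter. A spotter's lapse comes in only if it is read as the subject permitting unsafe use.
- *Forfeiture is discretionary.* The clause says that the device may be returned. That softens the incentive, but a subject cannot know in advance how the discretion will be used.
- *Not everyone has the same stake.* A reader might infer that every subject risks the full retail price. Purchase is one of three routes, and 13.1.2 records that one organisation has committed ten devices for veterans. The protocol does not say how many of those would go to subjects in this study.
- *Other sources exist.* They limit concealment, although none is stated to find these events.
- *Under-reporting is not shown.* A reader might infer that falls will be under-reported to a known degree. The protocol neither measures nor admits this, and it sets no zero-event criterion that a missing report would tip.
- *Documents not shown.* The consent forms (Appendix B) may already protect reports.

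A last argument is that 11.2.2 and 11.2.6 also give a reason to stay silent, since the same conduct can end sessions. That is true, and the change proposed here would not remove it. It would remove the added financial reason.

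**Conclusion.** The point holds in a limited form. A stated rule gives subjects who bought their device a financial reason not to disclose inadvertent unsafe use, in a study that relies mainly on them and a spotter they chose for the day-to-day home record. The direction of any bias follows from the text: fewer reports, and so more favourable answers on 3.3 and 3.4. The size does not. The upper limits of 22.1% to 44.2% rest on an assumed reporting probability between 1 and 0.5 applied to all twelve subjects. They fall to 24.0% at the high end if only two subjects own their device. They show that the matter could be material in a study this small, not that under-reporting will occur.

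Sections 11.3 and 13.1.1 also leave unclear who keeps a purchased device when the 11.3 condition is met. The change is worth making because it is cheap and protects two stated objectives; the design does not otherwise depend on it.

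**What to change.** 1. In 11.3, replace the words that make intent irrelevant with wording that limits loss without financial reconciliation to deliberate non-adherence or deliberate unsafe use. Merely deleting those words would not do, because the remaining condition would still cover unintended breaches.
2. Add to 11.3: *A fall, fault, deviation or other event that the subject or spotter reports in good faith does not by itself lead to loss of the device without financial reconciliation.*
3. Repeat both points in the subject and spotter consent forms, if they do not already say so.
4. Reconcile 11.3 with 13.1.1 on who keeps a purchased device.
5. At the existing three-monthly reviews (6.6), compare the logs with the device data already collected and record disagreements.

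The grounds for ending use in 11.2 and the sponsor's ability to recover an unsafe device stay as they are.

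Cost: a short amendment and possibly revised consent forms. The sponsor gives up a discretionary financial remedy for inadvertent, self-reported misuse, and may owe reimbursement if it recovers a purchased device. The log comparison is a small added task at each review.

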Physical Conditions	
 Temperature range 10-30 deg C Relative humidity range 20-95%, non-condensing Background sound pressure level: <70 dBA in the range of 100 Hz
Frequency of Use for Operator	
Maximum Frequency	6 hours per day

8. Recruitment Methods

8.1. Ekso Bionics will locate interested subjects from an existing group of prior test subjects. Additional networking for the purpose of identifying potential subjects will occur through rehabilitation hospitals currently using the Ekso Bionics device as well as non-for-profit organizations interested in supporting the individual use of Ekso. Since all recruitment will be verbal,

Protocol Name:	Investigational Study of the Ekso Bionics Powered Exoskeleton for High-Dosage Use by Individuals with Spinal Cord Injury in a Non-Clinical Environment
Principal Investigator:	[name], Sr. Controls Engineer
Primary Contact Name/Contact Info:	[name], Sr. Controls Engineer [contact] [contact]
Date Revised:	9/28/2015
Study Number:	13098-01

recruitment flyers or other marketing materials are not necessary. Hospitals acting as recruiting centers to locate Ekso Bionics test subjects may have their own IRB for recruiting only.

8.2. Ekso Bionics Clinical team members will perform the initial screening of potential participants. The team will determine study eligibility based on a clinical evaluation, home site evaluation, interviews with the prospective non-clinical spotter(s) and the experience and capability of the subject. They will discuss in detail the objectives, complete protocol, and its risks and potential benefits.

8.3. Once volunteers agree to participate they will be required to provide a medical release from their physician. Potential participants will read the Ekso Bionics informed consent and have an opportunity to ask questions and discuss the study with their physician, family, and friends before agreeing to enter the study. The informed consent and medical release (Appendix B) also include contact information should the participant or his/her associates have any questions. The original signed informed consent will be given to the participant, and a copy will be kept in a locked cabinet at Ekso Bionics accessible only by Investigators.

9. Number of Subjects

The study will consist of a minimum of two (2) subjects and a maximum of twelve (12).

10. Study Timelines

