Protocol Name:	Investigational Study of the Ekso Bionics Powered Exoskeleton for High-Dosage Use by Individuals with Spinal Cord Injury in a Non-Clinical Environment
Principal Investigator:	[name], Sr. Controls Engineer
Primary Contact Name/Contact Info:	[name], Sr. Controls Engineer [contact] [contact]
Date Revised:	9/28/2015
Study Number:	13098-01

The Investigational study will take place over the course of 36 months. Each subject will be evaluated for a minimum of 12 months during the 36 month period.

If at any point during the study, the subject must take a break from regular walking for medical or personal reasons, if the break is less than 2 month, they will be able to restart the study by notifying the principal investigator of the break and resuming use. If the break is greater than 2 months, the subject will need to be re-evaluated by an Ekso Bionics physical therapist to restart the study. In the case of a break of more than 2 months, the study clock will be considered "paused" at this point and the next evaluation after the initial re-evaluation will be 3 months later (+/- 2 weeks) if in the first year of the study and 6 months (+/- 2 weeks) after beyond the first year of the study.

11. Endpoints

11.1. At the conclusion of the 12-month training period, final measurements will be taken, both the subject and the non-clinical spotter will be interviewed or a questionnaire (Appendix C) will be provided to obtain information that will assist Ekso Bionics with further development of the device. Measurements will continue to be collected every 6 months for up to the conclusion of the study or the subject terminates his/her enrollment.

11.2. Sessions will be ended for any of the following reasons:

11.2.1. Subject decides to stop participation in the study at any time and for any reason.

11.2.2. An Ekso Bionics staff member stops the subject from taking part in this study at any time if he believes it is in the subject's best interest or if the subject does not follow the study protocol.

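### For a complete stop in device use of more than 21 days, Section 10 restarts the subject or pauses the clock while Section 11.4 withdraws the same subject

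*Protocol*

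**What the plan says.** Section 10 (Study Timelines) covers breaks from the subject's usual walking, at any point, for medical or personal reasons. For the shorter kind, "if the break is less than 2 month, they will be able to restart the study by notifying the principal investigator of the break" and taking up use again; no pause of the clock is mentioned. For the longer kind, a sponsor physical therapist must re-evaluate the subject before restart. The section continues: "In the case of a break of more than 2 months, the study clock will be considered" paused, and "the next evaluation after the initial re-evaluation will be 3 months later (+/- 2 weeks) if in the first year of the study", or 6 months later beyond the first year.

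Section 11.4 (Endpoints) has a separate rule for anyone who "does not walk in the Ekso for a period of more than 21 days for any reason, they will be withdrawn from the investigation". Section 11.4.1 adds that a subject who wishes to come back may do so, in which case "additional training of the subject and baseline assessments may be necessary".

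Section 10 also states: "Each subject will be evaluated for a minimum of 12 months during the 36 month period". Section 9 sets the sample at 2 to 12 subjects.

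**The concern.** A complete stop of more than 21 days for a medical or personal reason meets the conditions of both sections, and they assign the subject different statuses. Section 10 treats the subject as still in the study, either with the clock running or with it paused. Section 11.4 treats the subject as out, with a possible return on terms that 11.4.1 leaves open. Neither section refers to the other or says which prevails.

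These are conduct rules that staff apply from the protocol during the study, so they cannot wait for the analysis plan. Two people following the text correctly could record the same subject differently. At stake are the count of subjects retained, the label attached to each later visit, the date of the 12-month DEXA scan (bone density is measured only at baseline and 12 months), and possibly which baseline a change is measured from.

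**Working it through.** The protocol gives no figure on this point to reproduce. The check sets the break lengths side by side.

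Inputs: the 21-day limit (11.4); the 2-month boundary (Section 10), which is 59 to 62 days depending on the calendar months; 2 to 12 subjects (Section 9).

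| Length of complete stop | Section 10 | Sections 11.4 and 11.4.1 |
|---|---|---|
| Up to 21 days | Restart on notice; no pause stated | Not triggered |
| 22 days to just under 2 months | Restart on notice; no pause stated | Withdrawn; return possible, retraining and baseline assessments discretionary |
| Exactly 2 months | Neither branch applies | As in the row above |
| Over 2 months | Re-evaluation, clock paused, next evaluation 3 or 6 months after it | Withdrawn since day 22; same open terms of return |

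1. Up to 21 days the sections agree. The conflict starts at day 22.
2. The shortest 2-month break is 59 days, and 59 > 21. Every complete stop long enough to pause the clock has therefore already triggered withdrawal. If 11.4 is applied, no enrolled subject who has stopped entirely can reach the pause. If Section 10 is applied, the withdrawal in 11.4 is not carried out.
3. The 12-month DEXA scan could fall at three different times. It is 12 months from the first baseline if the clock ran on, and later by the length of the pause if the clock stopped. If the subject was withdrawn and re-baselined, it could be 12 months from the new baseline. Section 11.4.1 does not say whether that last schedule applies.
4. Weight of one case: 1/12 = 8.3% and 1/2 = 50%. In retention terms, 12 of 12 (100%) against 11 of 12 (91.7%), or 2 of 2 (100%) against 1 of 2 (50%).

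**The case against.** The strongest reply is that the sections can be read in sequence: the subject is withdrawn at day 22, gives notice, returns, and is retrained and reassessed if needed. Below 2 months this has some force. Section 10 speaks of restarting and 11.4.1 of resuming, no clock is paused, and a discretionary reassessment is compatible with return on notice. It still leaves open whether the subject counts as withdrawn, whether the visit clock kept running, and which baseline applies. Above 2 months it fails, because a paused clock does not describe someone who has left the study.

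A second reply is that the triggers differ: Section 10 concerns a break from usual walking, 11.4 no walking at all. But Section 10 makes restart depend on taking up use again, so complete stops are included, and the point is confined to those.

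A reader might also infer more than the text supports:

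- **Visits out of window.** The 2-week tolerance in Section 6.1 applies to reassessments that follow baseline. If a new baseline restarts the schedule, later visits are in window relative to it. Take an assumed 22-day stop from day 60, with a new baseline on day 82. The next visits fall near days 173, 265 and 356, each about 9 days from the 6-, 9- and 12-month visits of the first schedule (days 183, 274 and 365). For measures taken at every visit, this is mainly a change of label. Other start days and lengths give other offsets.
- **Loss of the first baseline.** Nothing says that a repeat overwrites it. Section 14.2 provides for keeping all data collected, and Section 14.5 for ten years' storage.
- **A duty to keep measuring after withdrawal.** The 12-month minimum in Section 10 does not say whether it covers a subject withdrawn under 11.4. Whether to assess people who no longer use the device is a separate design choice.

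It is also fair that this is an exploratory pilot with no stated hypothesis test for the conflict to bias.

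**Conclusion.** The contradiction stands, in current operative text, for complete stops of more than 21 days for medical or personal reasons. It is sharpest above 2 months, where the two rules cannot both be applied. Between 22 days and 2 months a sequential reading softens it but does not settle status, clock or baseline.

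One affected subject is 8% to 50% of the sample. The documents give no break rate, so the expected number of cases is unknown and no bias can be quantified. The effect on visit timing depends on whether a baseline repeated under 11.4.1 restarts the schedule, which the protocol does not say. The defect is one of wording, but in a study this small it can decide who counts as retained and when they are measured, so it should be corrected.

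**What to change.** Reconcile Sections 10, 11.4 and 11.4.1 into one rule, with cross-references, that states:

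- whether it covers complete non-use, reduced walking, or both;
- the subject's enrolment status and visit clock during and after a break, including a break of exactly 2 months;
- when baseline assessments are repeated, and that any repeat is recorded in addition to the first baseline.

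Report every enrolled subject with the date and reason of each break. The daily log (12.2.8) and the weekly device data transfer (12.2.2) should already supply much of this.

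The break length and the clinical handling of a subject who stops are for the sponsor and clinicians to decide. The choice of baseline for analysis can stay with the statistical analysis plan. The cost is a wording amendment.
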